- **Acceptance criteria: There must be at least a 90% probability that a user would respond with a score of 3 or higher to statements concerning instructions for use or ease of use.****

Study objectives 2.4 below are internal objectives and apply to data collected from all subjects OR subjects who have diabetes, as specified for each objective. The objectives apply to CONTOUR NEXT and CONTOUR TV3 BGMS as noted, and the results from the two meter systems will not be compared to each other.

2.4 Secondary Objectives (internal objectives):

2.4.1 Fingerstick Test (only subjects with diabetes): Obtain BGMS performance data in the hands of lay users with diabetes using fingerstick capillary blood obtained with Microlet NEXT lancing device.

CONTOUR NEXT:

- **95% of glucose results shall fall within ± 10.5 mg/dL of laboratory method at glucose concentrations < 100 mg/dL and within $\pm 10.5\%$ at glucose concentrations ≥ 100 mg/dL****

CONTOUR TV3:

- **95% of glucose results shall fall within ± 12.5 mg/dL of laboratory method at glucose concentrations < 100 mg/dL and within $\pm 12.5\%$ at glucose concentrations ≥ 100 mg/dL****

2.4.2 Study staff test (both BGMS; two analyses, one for all subjects and one for only subjects with diabetes): Obtain BGMS performance data in the hands of trained study staff testing subjects' fingerstick blood obtained with Microlet NEXT lancing device.

- **95% of glucose results shall fall within ± 15 mg/dL of laboratory method at glucose concentrations < 100 mg/dL and within $\pm 15\%$ at glucose concentrations ≥ 100 mg/dL*,****

2.4.3 Subject Questionnaire 2 (both BGMS; only subjects with diabetes): This questionnaire for subjects with diabetes will include statements about user preferences and feedback regarding the features of the BGMS in routine diabetes management. These statements will be given a rating by the subjects (1=strongly disagree, 2=disagree, 3=neutral, 4=agree, 5=strongly agree), and frequency distributions will be tabulated.

- **Acceptance criteria: There are no pass/fail criteria for Questionnaire 2.**

**This is a "total population" (hypothesis test) requirement for the pool of all subjects with diabetes.

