Objective	Sample Size, n	Critical Value, Xc	Po	Derivation of Critical Value*
2.1.1(95%), 2.2.1	350	333	96.65%	95% of n
2.1.1(9%)	350	347	99.61%	99% of n
2.3.1, 2.3.2, 2.3.3	315	300	96.79%	$\Pr\{\text{PASS} X_c, P_o\} \approx 95\%$
2.4.1	315	294	95.00%	$\Pr\{\text{PASS} X_c, P_o\} \approx 95\%$
2.4.2 (all subjects)	350	327	95.00%	$\Pr\{\text{PASS} X_c, P_o\} \approx 95\%$
2.4.2 (PWDs)	315	294	95.00%	$\Pr\{\text{PASS} X_c, P_o\} \approx 95\%$
2.2.2 (Questionnaire 1, All Subjects)	350	307	90.00%	$\Pr\{\text{PASS} X_c, P_o\} \approx 95\%$
2.3.4 (Questionnaire 1, PWDs)	315	276	90.00%	$\Pr\{\text{PASS} X_c, P_o\} \approx 95\%$
*Critical Values may change depending on actual sample size				

Note that error distribution tables will be constructed, to reflect the numbers and percentages of results falling within various error ranges (e.g., $\pm 5\%$, $\pm 7\%$, $\pm 10\%$, $\pm 12.5\%$, $\pm 15\%$, $\pm 20\%$). Tables will be by clinical site and overall.

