$$H_0: Pr\{response \geq 3\} < 90\% \text{ versus the alternative:}$$

$$H_a: Pr\{response \geq 3\} \geq 90\%$$

The critical number of responses greater than or equal to 3, X_c , is a function of the actual sample size, and will be chosen such that $0.95 = \sup Pr\{X \geq X_c | 100p\% = 90\%\}$. For example, if $n = 350$, then $X_c = 307$, so that $Pr\{X \geq X_c | 100p\% = 90\%\} \approx 0.9316 \leq 0.95$. That is, 307 is the number of responses ≥ 3 which yields the largest value of $Pr\{X \geq X_c | 100p\% = 90\%\} \leq 0.95$ for $n = 350$. For $n = 315$, the critical value is $X_c = 300$ (power ≈ 0.95).

11.4 Demographic, Diabetes History, Medications and Medical Conditions Data, Questionnaires 1 and 2

Descriptive statistics for Demographics, Diabetes History, Medications and Medical Conditions, and subject questionnaires will be computed as appropriate. Histograms will be constructed where appropriate. A percentage of subjects < 65 years of age will be calculated.

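### Section 11.3 gives 300 of 315 as the Questionnaire 1 pass mark for subjects with diabetes; Table 11.1 and section 11.3's own rule give 276 of 315.

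*Combined protocol and SAP*

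**What the plan says.** Objective 2.3.4 in section 2.3 sets the acceptance criterion for subjects with diabetes: "There must be at least a 90% probability that a user would respond with a score of 3 or higher". Section 11.3 turns this into a test with null hypothesis "H_0: Pr\{response \geq 3\} < 90"%. It says that the critical count depends on the actual sample size and is chosen so that "0.95 = \sup Pr\{X \geq X_c | 100p\% = 90"%. It then explains the rule in words: take the count with the largest pass probability at 90% that does not exceed 0.95.

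Two worked values follow. The first is "if $n = 350$, then $X_c = 307", with a pass probability of 0.9316. The second is "For $n = 315$, the critical value is $X_c = 300", with power of about 0.95.

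Table 11.1 in section 11.1 has a row for this objective that reads "2.3.4 (Questionnaire 1, PWDs) 315 276 90.00"%. In that table, 300 at n = 315 appears only in the row for the glucose accuracy objectives: "2.3.1, 2.3.2, 2.3.3 315 300 96.79"%.

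**The concern.** The questionnaire, the sample size and the 90% condition are the same in both places, but the pass marks are 300 and 276. Objective 2.3.4 is an explicit pass/fail criterion, it is assessed separately for each of the two meters, and each meter has its own ISO report (section 9.8). With two printed marks, the same responses can meet the objective or miss it according to which section the analyst reads. If the conflict is noticed only after the data are in, the choice of mark could look as though the result had driven it.

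**Working it through.** **Inputs**

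- True rate at the boundary: p = 0.90 (section 11.3 hypotheses; Po in Table 11.1).
- Sample sizes: n = 350 for all subjects and n = 315 for subjects with diabetes (section 11.1, Table 11.1).
- Rule (section 11.3): Xc is the smallest r with P(X ≥ r | n, p = 0.90) ≤ 0.95. This is the same as the largest pass probability not above 0.95.
- Printed marks at n = 315: 300 (section 11.3) and 276 (Table 11.1).

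**Formula.** With X binomial (n, p), P(X ≥ r) = Σ from k = r to n of C(n, k) p^k (1 − p)^(n − k), computed exactly.

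**Step 1: reproduce the plan's own example, n = 350, p = 0.90**

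- P(X ≥ 306) = 0.9510, above 0.95.
- P(X ≥ 307) = 0.9316, the first value not above 0.95.

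The rule gives 307, and both the count and the 0.9316 match section 11.3. The rule has therefore been read as the plan intends.

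**Step 2: apply the same rule at n = 315, p = 0.90**

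- P(X ≥ 275) = 0.9505, above 0.95.
- P(X ≥ 276) = 0.9299, the first value not above 0.95.
- P(X ≥ 300) = 0.0005.

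The rule gives 276, as Table 11.1 prints. The 300 does not follow from the rule, and its stated power of about 0.95 does not hold at 90%.

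**Step 3: look for another reading that yields 300**

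- A conventional one-sided 5% test against p = 0.90 at n = 315 gives 293 (P = 0.0404), not 300.
- At p = 0.9679, the Po of the accuracy row in Table 11.1, P(X ≥ 300) = 0.9502. Both the 300 and the 0.95 match that row. The likely explanation is that the accuracy figures were carried into the questionnaire section. This is an inference from the matching numbers; the documents do not say so.

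**Step 4: size of the disagreement, n = 315**

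As proportions, 276/315 = 87.6% and 300/315 = 95.2%; 300 − 276 = 24 responses. A count from 276 to 299 passes under one section and fails under the other, with probability P(X ≥ 276) − P(X ≥ 300).

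| True rate of scores ≥ 3 | Pass with 276 | Pass with 300 | Sections disagree |
|---|---|---|---|
| 90% | 0.930 | 0.0005 | 0.93 |
| 92% | 0.997 | 0.017 | 0.98 |
| 93% | 0.9998 | 0.068 | 0.93 |
| 95% | about 1 | 0.490 | 0.51 |
| 96% | about 1 | 0.802 | 0.20 |
| 97% | about 1 | 0.970 | 0.03 |
| 98% | about 1 | 0.999 | below 0.001 |

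The documents state no expected rate, so the table shows a range of assumed values.

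**The case against.** The strongest reply is that the rule, not the worked value, is the operative instruction. Section 11.3 says that the count will be chosen from the actual sample size, section 11.1 says that critical values may need adjusting, and the footnote to Table 11.1 repeats this. The 315 is only a planning figure: with 370 enrolled and 10 to 15% without diabetes, between 370 × 0.85 = 314.5 and 370 × 0.90 = 333 subjects would have diabetes. At n = 320 the rule gives 280 and at n = 330 it gives 289, so neither printed mark might be used. An analyst who follows the rule reaches a single answer. It can be added that this is a secondary ease-of-use objective, that a neutral score counts as a pass, and that at true rates of 97% or more the two marks almost always agree.

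Much of this is fair. It is more accurate to say that one printed value contradicts the rule and the table than that two thresholds have equal standing. The primary accuracy objective, the other accuracy criteria and the all-subjects questionnaire mark of 307 of 350 are unaffected. But the sample-size caveat cannot explain the gap, because n is 315 in both places. Nor does section 11.3's failure to label the 315 help: section 11.1 and Table 11.1 use that number only for subjects with diabetes, and 300 fails the rule whatever the group. The section that specifies the questionnaire test still prints a mark that its own rule does not give. High agreement rates may be plausible, but nothing in the documents supports relying on them.

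**Conclusion.** The concern holds: the pass mark of 300 of 315 in section 11.3 is wrong as written. The section's own rule and Table 11.1 both lead to 276. The power of about 0.95 attached to 300 is reached only at a true rate of about 96.79%, not at the 90% that defines the test.

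The practical effect depends on the unknown true rate: near-certain failure instead of a probable pass at 90%, and little difference at 97% and above. These figures rest on n = 315 and on independent responses with a common probability for the statement tested, which is the plan's own binomial model. It must be fixed, because it is a prespecified decision threshold stated in two incompatible ways.

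**What to change.** In section 11.3, replace the sentence on n = 315 with: for n = 315 (subjects with diabetes, objective 2.3.4), Xc = 276, with Pr{X ≥ 276 | p = 90%} = 0.930. Table 11.1 needs no change for this row. It would also help to add that, where the final n differs, Xc is recomputed by the rule in section 11.3 and the printed counts serve only as examples. The cost is a one-sentence amendment to the analysis section, made before the questionnaire data are analysed, with no effect on enrolment, procedures or data collection.

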11.5 Hematocrit Analysis

Hematocrit will be measured in singlet for each subject. Subjects with a hematocrit determination that is out of range cannot be used for blood glucose measurement comparisons.

Subject hematocrit measurement should be within 0-70% in order for the subject BG results to be considered evaluable for the ISO 15197 analysis. For the analysis according to the FDA SMBG: 2016, all subjects will be considered evaluable.

The mean, median, minimum, maximum, and standard deviation, will be computed for hematocrit determinations, for subjects with diabetes and for all subjects, by site and for both sites combined.

11.6 Temperature and Humidity

Means, medians, standard deviations, minimum and maximum room temperatures and humidities will be computed by site and for both sites combined.

11.7 Glucose distribution

The distribution of YSI glucose and a histogram (combined sites) for both capillary and venous blood will be provided. The mean, median, minimum, maximum, and standard deviation will be computed for glucose distributions, for subjects with diabetes and for all subjects, by site and for both sites combined.

In addition, the number of capillary samples with concentrations <80 and > 250 mg/dL will be reported.

11.8 Data Listing

A listing of the data (excel sheet) is needed for the CSR. The listing should include: subject and staff fingerstick meter results, AST (palm) meter results, venous meter results, capillary and venous mean YSI results, subject ID, hematocrit.

A listing of subject comments including subject IDs from the Ease of Use Questionnaire is needed for the CSR.

Note: If supplemental or unplanned analyses are requested, they will be presented in a supplemental report.

12.0 Administration

All investigator and site staff communications regarding the study should be directed to the Ascensia Study Manager. Please contact the Ascensia Study Manager noted below for any questions or problems concerning the clinical trial.

Documents to be collected prior to the start of the study include, but are not limited to:

- 1) CVs of Investigator and Sub-Investigators
- 2) Signature of PI on page 2 of protocol
- 3) IRB approval letter
- 4) IRB-approved ICF
- 5) Financial Disclosures for PI and Sub- Investigators
- 6) Clinical Trials Agreement (including Investigator Agreements for PIs and Sub-Investigators)
- 7) Site staff GCP training documentation

Data / documents to be collected during or after completion of the study include, but are not limited to:

- 1) EDC database
- 2) Progress Notes
- 3) Signature and Delegation Log (for all study staff)
- 4) Investigator's Report of Study Closure and IRB acknowledgement
- 5) Study-related training documentation

Appendix A - Instructions for Cleaning and Disinfecting Meters

Single-use items, such as test strips, test strip vials or lancing devices, shall not be used with multiple subjects and will be discarded in biohazardous containers after use. Blood glucose meters will be single-use, and will be cleaned and disinfected before returning to Ascensia by study staff only. Study staff will disinfect meters using the EPA-registered disinfectant noted in the UG and below that is suitable for use on hard, non-porous surfaces. Ascensia will provide the disinfectant.

EPA Registration	Manufacturer	Product Name	Active Ingredient
67619-12	Clorox Professional Products Company	Clorox Bleach Germicidal Wipes	0.55% sodium hypochlorite

1. Follow the manufacturer's directions printed on the container. Wear gloves.
2. If the meter is soiled, clean until all soil is removed before disinfecting.
3. Disinfect by wiping the meter with the disinfectant wipe until wet, and continue wiping for 60 seconds. Take care to prevent solution from running into the test strip port or around the buttons.
4. Dry the meter with a clean paper towel.
5. Dispose of all materials used in the cleaning and disinfecting procedure according to current lab biohazard procedures.

References

Protection of laboratory workers from occupationally acquired infections; approved guideline – third edition. CLSI document M29-A3. ISBN1-56238-567-4.

FDA, Processing/Reprocessing Medical Devices in Health Care Settings: Validation Methods and Labeling, May 2, 2011.

Appendix B - Instructions for Collection/Processing of Blood for YSI

Capillary Blood Collection

1. The study staff will perform a deep finger puncture using a Tenderlett, or similar, lancing device, on the subject's finger.
2. The study staff will express the blood and collect approximately 200 - 300 μ L in a blood collection tube (e.g. BD Microtainer with lithium heparin). A hand warmer may be used to improve blood flow and facilitate sample collection. Detailed instructions are as follows:
 - Typically the best finger to choose is the middle finger. It is recommended to practice the finger massaging technique prior to puncture.
 - Give subject a hand-warmer to hold for several minutes prior to puncture. Note that the hand-warmer should be moved to the subject's wrist when ready for puncture and kept there during the whole collection procedure.
 - Angle finger with tip slightly downward and squeeze fingertip gently prior to puncture.
 - Consider placement of finger puncture device: Choose a puncture site that will allow you to use your dominant hand to collect the blood. The device should be aligned so that the opening (where the blade comes out) is perpendicular to the grooves of the fingerprint and so that the opening is placed to the side of the finger (not too close to the nail).
 - While continuing to hold the fingertip, squeeze firmly, hold device firmly against side of finger and trigger the blade. Then turn the finger so that the nail is facing up.
 - Remove pressure from fingertip (to allow capillaries to fill with blood) and collect the first drop.
 - Begin massaging motion – continuous message of sides of the finger – this is critical.
 - Continue massaging finger from base to tip as you continue to collect the blood drops into the tube. If blood flow reduces it may help to press on the nail a bit in between massaging the finger. Having the subject stand up and drop their hand may also help.

Processing of Capillary or Venous Blood for YSI Analysis

1. Once collected, process the microtainer tube for laboratory glucose analysis as follows:
 - Label all tubes with the subject number and a C or a V (Capillary or Venous) as appropriate using a Sharpie marker. Also include a pre-determined notation for the capillary samples as to which meter test the sample corresponds (CONTOUR NEXT or CONTOUR TV3).
 - Gently invert the microtainer tube several times to mix the anticoagulant.
 - Centrifuge the whole blood immediately to separate the plasma from the red blood cells. Centrifugation must occur within 15 minutes of first meter blood test. Timing of all meter testing/centrifugation will be recorded on the appropriate CRF.
 - It is recommended that after centrifugation, the plasma is transferred from the microtainer tube to a micro/dispo tube or similar container. Ensure the container is labeled and the cap is secured.
 - The capped plasma sample may be kept at room temperature for up to 4 hours before testing.

2. If testing on the YSI Analyzer is not completed within 4 hours of sample collection, the plasma should be refrigerated for up to 24 hours, after which it should be frozen until the sample is tested.
3. Shipment of samples to Ascensia for glucose determinations may be recommended if YSI Analyzers do not meet the accuracy guidelines for the Ascensia traceability control sera. Arrangements will be made to ship the samples with dry ice via prepaid express mail should it become necessary.
4. Glucose values of the YSI replicates (controls and plasma) should be within 4 mg/dL or 4% of each other; if not, an additional assay should be run.
5. Insufficient (or suspected to be insufficient) samples, missing samples, and other sample issues should be recorded in the CRF and on the YSI printout as appropriate. If a sample is hemolyzed, record in the CRF.

Appendix C - Instructions for Hematocrit Sample Preparation & Testing

Staff performing the hematocrit will be trained in this procedure during the initiation visit by the study manager or designee.

1. Two hematocrit tubes will be obtained from each subject's blood. One tube will be measured and the result recorded on the form. The second tube will be measured only if the first tube was not adequate for measurement. Note:
 - Sample that is collected from venous blood will be collected in **un-treated micro-hematocrit tubes**.
 - Samples collected from capillary fingerstick blood will be collected in **treated micro-hematocrit tubes**.
2. Place a microhematocrit tube against the surface of the blood drop. Do not place the opening of the tube flush against the skin or it will be occluded.
3. Fill the microhematocrit tube about halfway. Do not over-fill. Then immediately place one of the microhematocrit tube openings in the clay sealant. Press into the clay 2-3 times to make sure enough sealant is transferred.
4. Place the sealed microhematocrit tube into the micro-centrifuge. Note: it is very important to place the microhematocrit tube in centrifuge rotor with clay side pointed outward. Spin for approx. 2 mins. Use dialed setting on StatSpin centrifuge.
5. Reading of hematocrit using StatSpin Crit-reader
 - After collection and centrifugation of hematocrit, place tube rotor in StatSpin Crit-reader, with clay side to the right.
 - Slide the marker on the crit-reader to the exact line where the clay and red blood cells meet (this is the "0" line). Press set button until "0" shows in the display.
 - Then move marker all the way over to the other end of the tube to the exact line where the plasma ends – press the set button until "100" shows in the display.
 - Now you are ready to read the hematocrit result. Slide the marker to the exact line where the red blood cells meet the plasma.
 - The result in the display is the hematocrit percentage for that sample.
6. An alternative to Step 5 is manual reading of the hematocrit by the operator using Manual StatSpin Micro Hematocrit Capillary Tube Reader.
7. Record hematocrit result on the appropriate form.

Appendix D - Hypoglycemia Protocol at AMCR Institute

AMCR Institute, Inc.

[contact]

[contact]

Email: [contact]

[name], CPI

Director

Hypoglycemia Protocol

I. **Objective:** To promptly reverse hypoglycemia in a consistent and therapeutically appropriate manner.

II. **Definition:** Hypoglycemia is a blood glucose that is ≤ 70 mg/dl even in the absence of obvious signs and symptoms. Signs and symptoms that may suggest hypoglycemia include: Shaky, sweaty, altered state of consciousness or personality change. The subject may report “I feel hypoglycemic”.

III. Procedure:

A: Conscious Patient without IV access in place:

1. Report all hypoglycemia to the supervising investigator immediately.
2. Treat with 15 gm of simple CHO. (Choose one)
 - Three or four Glucose tablets (preferred choice.)
 - 3/4 cup (6oz) of fruit juice (no sugar added)
 - 3/4 cup (6oz) of non-diet soda (Coke, Pepsi, 7-Up, etc.)
 - 1 cup of skim milk.
3. Repeat the blood glucose in 20 minutes and document. Notify the supervising investigator.
4. If the glucose is < 70 mg/dl after treatment.
 - Repeat 15 gm of simple carbohydrate.
 - Continue to perform blood glucose every 20 minutes and document results.
 - Continue to administer 15gm of simple carbohydrates every 20 minutes until the blood glucose is over 60 or until directed otherwise by the supervising investigator.

AMCR Institute SOP – Hypoglycemia Protocol

Approved: 1 December 2010 by [name]

AMCR Institute, Inc.

[contact]

[contact]

Email: [contact]

[name], CPI

Director

B. For all patients with IV access whether eating or NPO.

1. Treat with D50 if glucose is < 60 mg/dL. To determine the dose use this formula:

$(100 - BG) \times 0.3 = \text{Number of ml of D50W to push.}$

2. Notify the supervising investigator of the results.

3. Repeat the blood glucose 20 minutes after the treatment is provided and document results.

4. If the blood glucose is less than 60 mg/dl, repeat the D50 using the same dosing formula with the most recent glucose result.

C. Unconscious patients without IV access:

1. Treat with 1mg of Glucagon (adult dosage) IM or SQ. Notify the supervising investigator.

2. Patients receiving Glucagon may experience nausea and vomiting. It is imperative to turn the patient on their side during treatment to avoid aspiration.

3. Establish IV access and await further orders from the supervising investigator.

4. Repeat the blood glucose (BG) 20 minutes after the Glucagon dose to measure the drug's effectiveness and patient response to the medication.

IV. Documentation:

A. Document the administration of glucose tablets, juice, Glucagon, and D50 in the study chart

AMCR Institute SOP – Hypoglycemia Protocol

Approved: 1 December 2010 by [name]

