- 5.9.6 If adequate blood is not obtained from the first venipuncture attempt, up to 2 additional attempts are allowed if subject and study staff agree (total of up to 3 venipuncture attempts).
- 5.9.7 **If the time from meter test to blood centrifugation exceeds 15 minutes, the test is considered non-evaluable.** This will not be considered a protocol deviation. Times of meter tests and centrifugation will be recorded.
- 5.9.8 Hand warmers may be used throughout the testing to increase blood flow.
- 5.9.9 It is preferred that all fingerstick and AST lancings are from the same hand if possible, for each meter.
- 5.9.10 Study staff will record all meter results on the appropriate form. If meters have turned off, meter memory will be reviewed and the results will be obtained from meter memory.

- 5.9.11 Study staff will record every instance of second chance sampling by checking the box provided on the CRF.
- 5.9.12 Study staff will record in the comments section of the meter testing form, any obvious testing errors by the subject or staff as appropriate for staff tests, and any abnormalities observed in the testing procedure or BGMS.
- 5.9.13 Note that once the fingerstick testing is started in 5.7.1, the subject should not eat, or use medications until the capillary/AST testing is completed in 5.7.2 to avoid changing glucose levels. The subject can eat/take medicines at any time to avoid or treat hypoglycemia or hyperglycemia. If the subject eats or takes medications, results obtained after eating or medicating will be non-evaluable.

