7.2 Events related to hypoglycemia and hyperglycemia

Hypoglycemia and hyperglycemia can be a common occurrence with subjects who have diabetes.

If it is found that a subject has a hypoglycemic event, as determined by the Principal Investigator (PI) during a study visit, the subject will be treated by the site staff accordingly. Appendices D and E note each site’s treatment plan.

Classification of the hypoglycemic or hyperglycemic event is at the discretion of the PI or designee. If the hypoglycemic or hyperglycemic event is considered by the PI as an AE, it will be considered to be an anticipated AE and will be recorded on the AE Form.

Subjects who are hypo- or hyperglycemic may continue with fingerstick testing if they so choose, and if the PI determines that it is safe. The PI will define what is considered to be a hypoglycemic or hyperglycemic state.

Table 7.1: Classification of Adverse Event

Serious*	Non-Serious

An adverse event that leads to:
 
 a) death; b) a serious deterioration in health of the subject that, 
 1) resulted in a life-threatening illness or injury, 2) resulted in a permanent impairment of a body structure or a body function, 3) required in-patient hospitalization or prolongation of existing hospitalization, 4) resulted in medical or surgical intervention to prevent permanent impairment to body structure or a body function; c) fetal distress or a congenital abnormality or birth defect. 
May be anticipated or unanticipated.
 
*EN ISO 14155. Clinical investigation of medical devices for human subjects – Good Clinical Practice
	
All adverse events not reported as serious. At each visit, all adverse events observed by the investigator/designate or reported by subject must be evaluated and recorded on an adverse event form.
 
A non-serious adverse event is further classified with respect to severity and relationship to the trial product. A non-serious adverse event may be anticipated or unanticipated.
 
Further classification with regard to severity
 
 • Mild: Transient symptoms, easily tolerated, no interference with subjects daily activities. • Moderate: Marked symptoms, moderate interference with subjects daily activities, and tolerable. • Severe: Considerable interference with subject’s daily activities, not tolerable.

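### Appendix D, III.A: repeat carbohydrate stops by default above 60 mg/dL, although the same plan counts 70 mg/dL or below as hypoglycaemia

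*Combined protocol and SAP*

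**What the plan says.** Section 7.2 has site staff treat a hypoglycaemic event and refers to the two site appendices for how ("Appendices D and E note each" site's plan). It also leaves room for judgement: "The PI will define what is considered to be a hypoglycemic or hyperglycemic state".

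Appendix D is the plan for one of the two sites. Its objective is "To promptly reverse hypoglycemia in a consistent and therapeutically appropriate manner". Its definition in II is "Hypoglycemia is a blood glucose that is ≤ 70 mg/dl even in the absence of obvious signs and symptoms".

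Part III.A covers a conscious patient without IV access:

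- Step 1: "Report all hypoglycemia to the supervising investigator immediately".
- Step 2: give 15 g of simple carbohydrate.
- Step 3: recheck at 20 minutes and notify the investigator.
- Step 4 opens with "If the glucose is < 70 mg/dl after treatment". It then orders a further 15 g, glucose checks every 20 minutes, and continued 15 g doses of "simple carbohydrates every 20 minutes until the blood glucose is over 60 or until directed otherwise by the supervising investigator".

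**The concern.** The definition, the re-treatment trigger and the stop rule apply to the same subject within a few lines, and they use three different cut-offs. The stop rule is the one that matters most. If the investigator gives no other direction, staff who follow the page may end dosing in a subject whom the same page still calls hypoglycaemic.

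The stake is subject safety and the consistency of a written instruction. III.A is the branch most likely to be used: study procedures involve lancing and a single venipuncture, not an IV line, and 85 to 90% of subjects are to have diabetes (100% minus the 10 to 15% without it, Section 3.0). Low readings are also sought, since Section 5.6.1 sets each site a goal of about five fingerstick results below 80 mg/dL.

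**Working it through.** The plan gives no figure to reproduce. The check compares the thresholds directly, in whole mg/dL.

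| Element of Appendix D | Rule |
|---|---|
| Definition (II) | glucose ≤ 70 |
| Re-treatment trigger (III.A step 4) | glucose < 70 |
| Default end of repeat carbohydrate (III.A step 4) | glucose > 60 |

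**Overlaps as written**

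- Hypoglycaemic and past the stop rule: 61 to 70, so 70 − 61 + 1 = 10 readings.
- Meeting the re-treatment trigger and past the stop rule: 61 to 69, so 69 − 61 + 1 = 9 readings.
- Meeting the definition but not the trigger: 70 only, so 1 reading.

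**Following a subject through step 4**

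1. *Read in sequence.* A first recheck of 62 is below 70, so one more 15 g dose is given. If the next recheck is still 62, it is over 60 and dosing ends by default. A subject at 50 on the first recheck and 62 on the next also stops there. Both are at or below 70.
2. *Read as a loop,* with the trigger applied at every recheck. A reading of 62 then orders another dose (below 70) and ends dosing (over 60) at the same time.
3. *A first recheck of exactly 70.* The subject is hypoglycaemic under II, but step 4 is not triggered and no repeat dose is ordered.

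Neither reading of step 4 makes the thresholds agree.

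**After changing the stop to > 70 and the trigger to ≤ 70**

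- Hypoglycaemic (≤ 70) and past the stop (> 70): 0 readings.
- Meeting the trigger (≤ 70) and past the stop (> 70): 0 readings.
- Meeting the definition but not the trigger: 0 readings.

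**Who is exposed.** Only treated, conscious subjects without IV access at this site, and only when the investigator does not direct otherwise. The documents do not allow a count. The goal of about five results below 80 mg/dL is not a cap, counts laboratory results rather than treated subjects, and includes readings of 71 to 79 that Appendix D does not call hypoglycaemia.

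**The case against.** The strongest case on the other side is that this is a narrow path under active medical oversight, and that 60 may be a deliberate clinical choice.

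- **Oversight.** To reach the default stop, a subject must have had at least two 15 g doses (steps 2 and 4) and read above 60. The investigator must have been told at the start and again at the recheck, and then given no direction. The 20-minute checks in step 4 carry no 60 mg/dL endpoint, so monitoring does not stop with the carbohydrate. Section 5.9.13 adds "The subject can eat/take medicines at any time to avoid or treat hypoglycemia or hyperglycemia". All of this stands and limits the harm. It does not change what the page tells staff to do when no other direction comes.
- **The PI may define the hypoglycaemic state (7.2).** True, but the written site plan commits to 70 or below. Even with the definition set aside, the below-70 trigger and the above-60 stop conflict within one step.
- **Use of 60 elsewhere.** III.B also acts at 60, but for intravenous dextrose in patients with IV access. It does not explain an oral stop set below the oral trigger.
- **Appendix E.** The other site's plan is permissive too: it observes asymptomatic subjects at 50 to 69 and lets repeat dosing end once glucose is increasing. However, it requires treatment if glucose has not reached 70 after 2 hours. Appendix D treats regardless of symptoms and has no such backstop.
- **Ambiguity.** Step 4 can be read as a loop, so an early stop is not the only reading. This is fair, but the alternative is two contradictory orders.

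The documents do not show whether 60 is a slip or a judgement. That is a reason to have the site investigator confirm the values, not to leave the text as it is.

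**Conclusion.** The point holds. In III.A of Appendix D the default end of repeat carbohydrate is 10 mg/dL below the upper limit of the plan's own definition of hypoglycaemia (70 − 60 = 10). Ten whole-number readings are affected, nine of them also under a conflicting order to re-treat. There is a further one-reading gap at exactly 70 between the definition and the trigger.

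This rests on three conditions: readings in whole mg/dL, the definition in II applying as written, and no contrary direction from the investigator. How often they occur together cannot be estimated from the documents.

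The accuracy analysis is untouched: no sample size, critical value or acceptance criterion depends on these thresholds. The correction should be made as a matter of subject safety and internal consistency. The safeguards already in place keep it from being more serious than that.

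**What to change.** In Appendix D, III.A step 4:

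1. Change the stop value from over 60 to over 70 mg/dL and keep the investigator override.
2. Change the re-treatment trigger from below 70 to 70 mg/dL or below, to match II.
3. Have the site investigator confirm both values before enrolment begins.

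These edits align III.A only. III.B would still use 60 for patients with IV access; the investigator can be asked at the same time whether that is intended.

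The cost is two numbers on one page of a site procedure, plus the site's confirmation. The appendix belongs to a protocol whose version the IRB approves (Section 9.2), so the corrected page should go through the usual document control. Nothing in the statistical sections needs to change.
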